9.1.5 Body weight

Body weight will be measured in kilograms and collected in the eCRFs every 3 months throughout the duration of the study, as well as at the “end of study visit”. More frequent weight may be obtained at the discretion of the Investigator.

9.1.6 Electrocardiogram variables

Standard 12-lead ECGs are recorded after at least 15 minutes in the supine position using an electrocardiographic device. The following will be assessed: heart rate, rhythm, interval between the peaks of successive QRS complexes (RR), interval from the beginning of the P wave until the beginning of the QRS complex (PR), interval from start of the Q wave to the end of the S wave (QRS), interval between the start of the Q wave and the end of the T wave (QT), QT interval corrected for heart rate (QTc) automatic correction evaluation (by the ECG device), QRS axis, R voltage V6, voltage V1, left ventricular hypertrophy criteria, right ventricular hypertrophy criteria, repolarization charges, and overall cardiac impression for each patient.

Each ECG consists of a 10-second recording of the 12 leads simultaneously, leading to:

- A single 12-lead ECG (25 mm/s, 10 mm/mV) printout including date, time, initials, and number of the patient, signature of the research physician, and at least 3 complexes for each lead. The study site cardiologist’s medical opinion and automatic values will be recorded in the eCRF. This printout will be retained at the site.
- A single digital file will be stored which enables manual reading when it is necessary (centralized reading of computerized ECGs); each digital file will be identified by theoretical time (day and time), real date and real time (recorder time), and patient number (eg, 3 digits) and initials (eg, 3 digits). The digital recording, data storage, and transmission (whenever requested) need to comply with all applicable regulatory

requirements (ie, US Food and Drug Administration [FDA] Code of Federal Regulations, Title 21, Part 11).

The qualified Investigator or appropriate designee (qualified physician) should review the ECGs in a timely manner to determine if there are any safety concerns and for clinical management of the patient. In the event of any clinically significant abnormal findings that meet the definition of an AE (see [Section 10.4.1](#) for definitions and reporting), the Investigator will continue to monitor the patient with additional ECGs until the ECG returns to baseline or the Investigator determines that follow-up is no longer necessary.

In case of abnormal findings by the qualified Investigator, the ECG should be provided to the study site cardiologist for further confirmation and description of findings.

All ECGs will also be collected and read centrally by a third-party independent reviewer.

9.1.7 Immunogenicity

Immunogenicity assessments will include the following:

- Samples will be collected from patients and evaluated for anti-avalglucosidase alfa antibodies every month during the first 6 months and then every 3 months throughout the duration of the study. ADA seropositive patient serum will be assessed for neutralizing antibodies to avalglucosidase alfa which may include inhibition of enzyme activity and uptake.
- Samples will be collected from patients who were previously treated with alglucosidase alfa and evaluated for anti-alglucosidase alfa IgG antibodies every 6 months for up to the first 6 years of the study.
- Samples will be collected from patients and evaluated for IgE, complement activation, serum tryptase following moderate, severe, or recurrent mild IARs suggestive of hypersensitivity reactions ([Section 8.8.2](#)).
- In the event a patient exhibits signs or symptoms suggestive of systemic immune-mediated reactions involving skin and other organs while receiving alglucosidase alfa, serum samples are obtained for the evaluation of circulating immune complexes.
- Leftover antibody samples will be stored for further analysis as needed.
- See the study-specific laboratory manual as well as the Study Operations Manual (SOM) for guidelines on the collection and shipment of antibody and IAR samples and circulating immune complex samples.

9.2 PHARMACOKINETICS

9.2.1 Sampling times

Blood samples for evaluation of avalglucosidase alfa PK will be collected before, during, and after avalglucosidase alfa infusions at 6 months and then yearly thereafter for the first 6 years.

Sampling times are as follows: pre-dose (prior to infusion), at the end of the infusion, and at 1, 4, 8, 12, and 24 hours after infusion. The following PK blood samples are to be collected within 15 minutes of scheduled time: pre-dose and all samples immediately following the end of the infusion through 8 hours post infusion. Pharmacokinetic samples collected 12 hours through 24 hours post infusion are to be collected ± 2 hours of the scheduled time.

9.2.2 Number of pharmacokinetic samples

The number of PK samples will vary by patient depending on the length of the patient's participation in the extension study.

9.2.3 Sample handling procedure

Special procedures for collection, storage, and shipment will be provided in the study- specific laboratory manual.

9.2.4 Bioanalytical methods

Plasma samples will be analyzed using validated, sensitive and specific bioanalytical methods, namely, a fluorometric assay using a 4-methylumbelliferyl- α -D-glucoside (4-MUG) substrate to detect avalglucosidase alfa activity.

9.2.5 Pharmacokinetic parameters

The following PK parameters will be calculated, using noncompartmental methods from plasma avalglucosidase alfa concentrations obtained after single and repeat dose administration. The parameters will include, but may not be limited to the following list in [Table 4](#).

Table 4 - List of pharmacokinetic parameters and definitions

Parameters	Drug/Analyte	Matrix	Definition/Calculation
C_{max}	avalglucosidase alfa	Plasma	Maximum plasma concentration observed
AUC_{last}	avalglucosidase alfa	Plasma	Area under the plasma concentration versus time curve calculated using the trapezoidal method from time zero to the real time
			Area under the plasma concentration versus time curve extrapolated to infinity according to the following equation:
AUC	avalglucosidase alfa	Plasma	$AUC = AUC_{last} + \frac{C_{last}}{\lambda_z}$ Values with a percentage of extrapolation >20% will not be taken into account in the descriptive statistics
t_{last}	avalglucosidase alfa	Plasma	Time corresponding to the last concentration above the limit of quantification, C_{last}
			Terminal half-life associated with the terminal slope (λ_z) determined according to the following equation:
$t_{1/2z}$	avalglucosidase alfa	Plasma	$t_{1/2z} = \frac{0.693}{\lambda_z}$ where λ_z is the slope of the regression line of the terminal phase of the plasma concentration versus time curve, in semi-logarithmic scale. Half-life is calculated by taking the regression of at least 3 points.
CL	avalglucosidase alfa	Plasma	Apparent total body clearance of a drug from the plasma calculated using the following equation:
			$CL = \frac{Dose}{AUC}$
V_d	avalglucosidase alfa	Plasma	Apparent Volume of Distribution during the terminal (λ_z) phase calculated using the following equation:
			$V_z = \frac{CL}{\lambda_z}$

9.3 PHARMACODYNAMIC PARAMETERS

9.3.1 Skeletal muscle magnetic resonance imaging

Skeletal muscle MRI will be performed prior to the muscle needle or open biopsy procedure. Skeletal muscle MRI images obtained within LTS13769 study will be analyzed using muscle MRI images obtained as baseline from previous study. Magnetic resonance imaging will be processed and analyzed centrally. A protocol for MRI acquisition and analysis will be provided in the study-specific manual.

9.3.2 Skeletal muscle biopsy

Muscle biopsy is not required in patients in whom the prior muscle biopsy, obtained in a prior avalglucosidase alfa study, had a glycogen content <5% unless the patient shows significant clinical decline. Needle or open biopsy of the lower extremity (quadriceps) muscle will be performed following the skeletal muscle MRI. The MRI appearance of the muscle will be used to determine the level (axial slice position) that the biopsy procedure should target (avoiding fatty replaced tissue). Glycogen content will be measured by histomorphometric analysis or severity grading to determine how effectively avalglucosidase alfa is able to remove glycogen from muscle.

Further instructions regarding the biopsy sampling and the collection and shipment of biopsy samples will be provided in the study-specific laboratory manual.

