5.2 SECONDARY

The secondary objective is to assess the long-term effect of avalglucosidase alfa on pharmacodynamic and exploratory efficacy variables to assess if the benefits of avalglucosidase alfa are maintained and to assess the time course of response.

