10.1.2.6 Every 2 years

The following assessments will be performed every 2 years:

- MRI.
- Skeletal muscle biopsy (not required in patients in whom the prior muscle biopsy, obtained in a prior avalglucosidase alfa study, had a glycogen content <5% unless the patient shows significant clinical decline).
- Serum sample collection for skeletal muscle RNA expression analyses (not required in patients in whom the prior muscle biopsy, obtained in a prior avalglucosidase alfa study, had a glycogen content <5% unless the patient shows significant clinical decline).

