10.1.2.7 Re-baseline visit

The following assessments will be performed at the re-baseline visit after having obtained informed consent and before receiving the higher dose.

The “Re-baseline” will only apply to patients who have switched from 5 or 10 to 20 mg/kg. If the patient changes dose from 5 or 10 mg/kg to 20 mg/kg qow dose, the visit dates need to be adapted accordingly (see [Section 1.2](#)).

Results from selected previous assessments may be used and the assessment does not need to be repeated at the re-baseline visit depending on the last available assessment date:

- Physical examination (within 1 month).
- Urine pregnancy test (females only).
- Body weight.
- Vital signs.
- ECG (within 1 month).
- Hematology and urinalysis (within 1 month).
- Biochemistry.
- Anti-avalglucosidase alfa antibodies and neutralizing antibodies in ADA-positive patients.
- Anti-alglucosidase alfa IgG antibodies (only patients who were previously treated with alglucosidase alfa).
- Avalglucosidase alfa PK plasma sample collection (within 6 months).
- MRI (within 6 months).
- In patients in whom the prior muscle biopsy, obtained in a prior avalglucosidase alfa study, had a glycogen content >5% or who show significant clinical decline:
 - Skeletal muscle needle or open biopsy (within 6 months),
 - Serum sample collection for skeletal muscle RNA expression analyses (within 6 months).

- Urine Hex4 sample collection (within 1 month).
- Exploratory biomarker urine sample collection (within 1 month).
- Exploratory biomarker plasma sample collection (within 1 month).
- 6MWT (within 1 month).
- PFT (within 1 month).
- Plasma sample collection for microRNA analyses (within 1 month).

10.1.2.8 *Patient temporarily discontinued from study treatment while remaining in the study*

- In case of temporary treatment discontinuation of study drug the visits and assessments will be adapted to the absence of infusion of avalglucosidase alfa until the patient resumes treatment within the study:
 - Study visits can be adapted to every 4 weeks or when laboratory and/or clinical testing are scheduled, as long as the assessment time windows in the study protocol are respected. Patients should adhere to original target infusion and visit schedule based on first infusion in LTS13769 or first infusion of 20 mg/kg in the LTS13769 study.

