10.1.3.7 End of study visit

The following will be performed at the end of study visit:

- Physical examination.

- Urine pregnancy test (females only).
- Body weight.
- Vital signs.
- ECG.
- Hematology and urinalysis.
- Biochemistry.
- Anti-avalglucosidase alfa antibodies and neutralizing antibodies in ADA-positive patients.
- MRI.
- In patients in whom the prior muscle biopsy, obtained in a prior avalglucosidase alfa study, had a glycogen content >5%, or who show significant clinical decline:
 - Skeletal muscle needle or open biopsy (within 6 months),
- Urine Hex4 sample collection.
- Exploratory biomarker urine sample collection.
- Exploratory biomarker plasma sample collection.
- 6MWT.
- PFT.
- Plasma sample collection for microRNA analyses.
- Infusion of avalglucosidase alfa.

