2.4.7 Analyses of pharmacodynamic variables

Pharmacodynamic variables are described in [Section 2.1.6](#).

Descriptive statistics (including mean, SD, median, minimum, maximum, and 95% confidence intervals (CI) of changes) for both observed and change from baseline (and/or rebaseline, if specified) by study visit will be provided for quantitative parameters, by group and by each patient group/dose level, unless otherwise specified. Qualitative results that are categorical will be presented with number and percentage of patients in each category. If a linear trend in the change of a pharmacodynamic endpoint is observed, a longitudinal model may be employed to model change from baseline over time.

Muscle MRI

MRI data collected from the TDR12857 and LTS13769 studies will be summarized separately, due to the updated methods used for LTS13769. The Week 27 results from TDR12857 will be used as the LTS13769 baseline for LTS13769 study (see [Section 2.5.1](#)). Descriptive statistics will be used for quantitative parameters to summarize changes over time from baseline/rebaseline for each study. The Mercuri grading will be presented both as a categorical variable (ie, number and percentage of patients in each grade over time will be presented) and as a continuous variable (ie, number, mean, SD, median, minimum, maximum, and 95% CI will be presented at each visit). Additional summaries will be presented for the patients previously allocated to the 5 or 10 mg/kg dose groups in the TDR13857 study and switched to 20 mg/kg in the LTS13769 study (see [Section 2.5.1](#)). The number of patients with abnormally high values for any specific muscle, as indicated by a T2 of >39 ms, will be presented using descriptive statistics.

Muscle biopsy

Changes from the TDR12857 baseline over time will be used to summarize continuous variables. For qualitative measures, number and patients in each category over time will be presented.

A correlative measure comparing the biopsied muscle and its MRI counterpart will also be performed.

Urine Hex4

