Week 11 in TDR (71)	Week 11	64 to 77 days
Week 13 in TDR (85)	Week 13	78 to 91 days
Week 15 in TDR (99)	Week 15	92 to 105 days
Week 17 in TDR (113)	Week 17	106 to 119 days
Week 19 in TDR (127)	Week 19	120 to 133 days
Week 21 in TDR (142)	Week 21	134 to 148 days
Week 23 in TDR (156)	Week 23	149 to 162 days
Week 25 in TDR (169)	Week 25	163 to 176 days/(1 st day of LTS – 1)**
Month 6 in LTS (365)	Week 52	(1 st day of LTS) to 548 days
Month 18 in LTS (730)	Week 104	549 to 913 days
Month 30 in LTS (1095)	Week 156	914 to 1278 days
Month 42 in LTS (1460)	Week 208	1279 to 1643 days
Month 54 in LTS (1825)	Week 260	1644 to 2008 days
Month 66 in LTS (2190)	Week 312	2009 to 2373 days
Month 72 in LTS (2372)	Week 338	2374 to 2402 days

*Study days are days since the first infusion in the TDR12857 study.

**For patients who enrolled in LTS13769, the upper boundary of the window is 176 days or (1st day of LTS – 1), whichever is earlier; for patients who didn't enroll in LTS13769, use study day 176 as cutoff.

Table 6 – Plasma concentration of avalglucosidase alfa

VISIT (target study day*)	Analysis Visit	Analysis Visit Window (in study days*)
Baseline	Baseline	
Week 1 in TDR (1)	Week 1	1 to 42 days
Week 13 in TDR (85)	Week 13	43 to 127 days
Week 25 in TDR (169)	Week 25	128 to 273 days/(1 st day of LTS – 1)**
Month 6 in LTS (365)	Week 52	(1 st day of LTS) to 548 days
Month 18 in LTS (730)	Week 104	549 to 913 days
Month 30 in LTS (1095)	Week 156	914 to 1278 days
Month 42 in LTS (1460)	Week 208	1279 to 1643 days
Month 54 in LTS (1825)	Week 260	1644 to 2008 days
Month 66 in LTS (2190)	Week 312	2009 to 2373 days
Month 72 in LTS (2372)	Week 338	2374 to 2402 days

*Study days are days since the first infusion in the TDR12857 study.

**For patients who enrolled in LTS13769, the upper boundary of the window is 273 days or (1st day of LTS – 1), whichever is earlier; for patients who didn't enroll in LTS13769, use study day 273 as cutoff.

Table 7 –MRI, muscle biopsy

VISIT (target study day*)	Analysis Visit	Analysis Visit Window (in study days*)
Baseline	Baseline	
Week 27 in TDR (184)	Week 27	92 to 273 days/(1 st day of LTS – 1)**
Month 24 in LTS (365)	Week 52	(1 st day of LTS) to 1278 days
Month 48 in LTS (1095)	Week 156	1279 to 2008 days
Month 72 in LTS (2372)	Week 338	2009 to 2402 days

*Study days are days since the first infusion in the TDR12857 study.

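### The biopsy exemption changes which patients supply muscle glycogen data between TDR12857 and LTS13769, and the SAP's change-from-baseline summary does not allow for it

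*Protocol*

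**What the plan says.** Protocol 9.3.2 excuses from biopsy any patient whose earlier-study sample "had a glycogen content <5% unless the patient shows significant clinical decline". Section 10.1.2.6 repeats the rule for the two-yearly visits. Sections 10.1.2.7 (re-baseline) and 10.1.3.7 (end of study) state it the other way round: biopsy applies where the prior-study sample "had a glycogen content >5% or who show significant clinical decline".

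SAP Appendix B, Table 7, lists biopsy visits at TDR12857 baseline and Week 27, then in LTS13769. For the analysis, SAP 2.4.7 says: "Changes from the TDR12857 baseline over time will be used to summarize continuous variables". Graded results are counted per category over time. SAP 2.3.3 admits any patient with any pharmacodynamic data and no critical dosing deviation. SAP 2.5.3 plans no imputation and by default leaves patients with missing data out of percentages. A longitudinal model is optional, conditional on seeing a linear trend, and not specified.

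Glycogen serves the secondary objective, which is "to assess if the benefits of avalglucosidase alfa are maintained and to assess the time course of response" (Protocol 5.2). The 2023 erratum removes exploratory efficacy from that objective but keeps pharmacodynamics, and it keeps biopsy as a secondary endpoint.

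**The concern.** The value of the outcome, or later clinical worsening, decides who must be measured again. At the TDR12857 visits the biopsy summary covers everyone who was sampled. At the LTS13769 visits the required sample is patients who were not below 5%, plus patients below 5% who have since declined. A by-visit summary then joins two differently composed groups in one time course, and the step between them can be read as a change in glycogen.

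I found nothing in SAP 2.4.7 that compares the same patients with their own Week 27 value, separates biopsies by reason, or counts exempt patients. At stake is the reading of whether glycogen clearance is maintained, which is what this endpoint is there to show. Severity grades are affected too: exempt low-glycogen patients would drop out of the denominator, shifting the percentages towards the worse grades.

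**Working it through.** The plan gives no figure to reproduce: there is no sample-size calculation, glycogen distribution or share of patients below 5%. All glycogen values below are assumptions.

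**Algebra.** Let a fraction p of patients be biopsied later (R) and 1 − p be exempt (E). Let m be the mean glycogen at Week 27 and c the mean change from baseline to Week 27 in each group. If nobody changes after Week 27 and there is no measurement error:

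- Step in the observed mean = m_R − [p·m_R + (1 − p)·m_E] = (1 − p)(m_R − m_E). Without decliners, every value in R is at least 5% and every value in E is below 5%, so the step is upward.
- Step in the mean change = (1 − p)(c_R − c_E). Its sign depends on which group had the larger fall. The rule does not settle that, because the cutoff is an absolute level and not a response.

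**Two hand examples**, both with p = 0.5 and a Week 27 mean change of −4.5, chosen only to show the sign:

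- Half go from 12 to 3 and half stay at 12. Week 27 change = (−9 + 0)/2 = −4.5; later change in those not exempt = 0. Observed mean goes from 7.5 to 12. This is an extreme case, with complete non-response in half the patients.
- Half go from 12 to 6 and half from 6 to 3. Week 27 change = (−6 − 3)/2 = −4.5; later change in those not exempt = −6. Observed mean goes from 4.5 to 6.

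**Simulation**, 1,000,000 patients per scenario, true glycogen frozen after Week 27. Assumed inputs:

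- median baseline 5% or 8%, log-SD 0.6;
- Week 27/baseline ratio with (median, log-SD) of (1.0, 0.5), (0.8, 0.2), (0.8, 0.7), (0.5, 0.2) or (0.5, 0.7);
- measurement error 0, 0.3 or 0.6 on the log scale;
- later biopsy if measured Week 27 glycogen was at least 5%, plus a random 10% as decliners.

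That gives 2 × 5 × 3 = 30 scenarios. Four of them, all with error 0.3:

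| Baseline; ratio; log-SD | Share biopsied later | Week 27 mean, all | Later mean | Week 27 change, all | Later change | Same patients, later minus Week 27 |
|---|---|---|---|---|---|---|
| 8; 0.5; 0.7 | 45% | 6.12 | 10.20 | −3.47 | −2.20 | −0.36 |
| 5; 0.5; 0.7 | 30% | 3.83 | 7.53 | −2.16 | −0.71 | −0.41 |
| 8; 0.5; 0.2 | 42% | 4.88 | 7.25 | −4.70 | −6.50 | −0.51 |
| 5; 0.8; 0.2 | 42% | 4.89 | 7.25 | −1.10 | −1.35 | −0.53 |

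Over all 30 scenarios, 22% to 75% of patients were still biopsied.

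- Observed mean: higher than the full-cohort Week 27 mean in 30 of 30, by 1.5 to 4.3 points.
- Mean change from baseline: less favourable in 18 of 30 (all those with variable response, log-SD 0.5 or 0.7) by about 1.0 to 2.3 points; more favourable in 12 of 30 (near-uniform proportional response, log-SD 0.2) by about 0.2 to 2.0 points.
- Same patients, later minus own Week 27 value: 0 without measurement error, −0.3 to −1.8 with it. The paired comparison shows no false loss, but it regresses downward because patients were selected on the Week 27 value.

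Decliners were drawn at random, so any extra effect of selecting on clinical worsening is not counted.

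**The case against.** Much of the case on the other side stands, and it limits what can be claimed.

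- A reader might infer that every visit compares different patients. The text does not support that. The exemption is tied to the biopsy from the prior study, not to the latest one, so it is a fixed status. The main break is the single one between the studies; afterwards the required set shifts only through decliners and dropout.
- A reader might infer that the best responders leave, so the curve must drift towards lost benefit. The cutoff is a level: a patient with little storage at baseline and little change is also exempt. For change from baseline, the bias can favour either reading.
- A reader might infer that patients below 5% are never biopsied unless they decline. The wording is that a biopsy is not required, which does not forbid one. Actual selection may be weaker.
- That Week 27 is the deciding biopsy is inferred from SAP Table 7, a table of visit windows. The TDR12857 protocol is not among the documents.
- Part of the protection exists. Change from baseline uses each patient's own baseline, Protocol 11 calls for n at each time point and patient listings, and SAP 2.5.3 allows missing counts to be shown where relevant. Urinary Hex4 and MRI, scheduled without this exemption, also bear on maintenance.

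None of this supplies a same-patient Week 27 reference or shows why n falls. Each patient's own baseline does not remove the problem, because the artefact lies in whose changes are averaged.

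**Conclusion.** The point holds in this form: followed as written, SAP 2.4.7 joins a full biopsied cohort in TDR12857 to one selected on the outcome in LTS13769, so the glycogen time course can misstate whether benefit is maintained. With no true change after Week 27, a higher observed mean is expected; the direction for mean change from baseline depends on how response varies with baseline. The simulated sizes illustrate this under assumed distributions and are not estimates for this trial. The conclusion also rests on the exemption being used in practice and on Week 27 being the deciding biopsy.

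The endpoint is secondary, descriptive and untested, so what suffers is interpretation and not an error rate. The summary alone should not be used to claim either that clearance was maintained or that it was lost.

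A small side point: Protocol 9.3.2 and 10.1.2.6 exempt values below 5%, while 10.1.2.7 and 10.1.3.7 call for biopsy above 5%. A value of exactly 5% is treated differently by the two forms, so the passages should be reconciled.

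**What to change.** In SAP 2.4.7, under muscle biopsy:

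1. For each LTS13769 visit, restate the baseline and Week 27 (last prior-study) means and changes for the same patients who contribute to that visit.
2. Identify biopsies done because of clinical decline in otherwise exempt patients, in a listing if numbers are small, and keep them out of the main time-course row.
3. At each visit, give the number of exempt patients with their last glycogen value. For severity grades, show them as a separate category instead of dropping them from the denominator.
4. State that LTS13769 biopsy summaries do not represent the whole treated population, and that change from the Week 27 value in patients selected on that value is subject to regression to the mean in the drug's favour.

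The exemption stays as it is and no biopsy is added. The cost is SAP wording and one restructured table. The downside is smaller numbers per row, in a study the SAP itself describes as having few patients, and a narrower claim about long-term glycogen clearance.
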